After the baseline period, participants returned once monthly (every 30 +/- 3 days) for up to 10 additional visits to the CCTS CRU for dispensation of their placebo or botanical capsule kits. At visits 4, 7, and 10, participants received additional blood draws to monitor liver and kidney function (sodium, potassium, chloride, bicarbonate, anion gap, glucose, blood urea nitrogen (BUN), creatinine, calcium, phosphorus, albumin, total protein, total bilirubin, direct bilirubin, indirect bilirubin, alkaline phosphatase, aspartate aminotransferase (AST), and alanine aminotransferase (ALT)). Participants were compensated for each laboratory visit.

For each botanical, participants followed the same protocol: one month (30 +/- 3 days) of placebo, one month (30 +/- 3 days) of lower-dose botanical, and one month (30 +/- 3 days) of higher-dose botanical. Study participants were blinded to both the assigned botanicals and

administration protocol (placebo, lower-dose, higher-dose). This administration order was chosen for safety reasons, i.e., adverse effects could be detected in a lower-dose condition before a higher-dose, with possibly greater adverse effects, would be administered. Research personnel were blinded to the assigned botanicals but not to the administration protocol. The study pharmacist was unblinded to both administration protocol and assigned botanicals but had no contact with study participants. Adherence to botanicals was checked at each study visit when participants returned their used blister packs. If participants had missed doses, study staff reminded them of the importance of a regular dosing schedule.

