2.7. Statistical Analyses

Analyses were conducted using SPSS Statistics for Windows, version 24 (IBM Corp., Armonk, NY, USA). Effects of botanicals on symptom severity were tested using separate twolevel linear mixed models (LMM). LMMs are designed for nested data structures and allow for the dependence between observations typically seen with repeatedly measured variables. In this study, longitudinal outcome assessments are nested within individuals and conditions, violating the assumption of independence between observations. For each botanical, three models were built with condition (baseline, placebo, lower-dose, and higher-dose) entered as a fixed factor and symptom severity (GWI, pain, or fatigue) as the dependent variable, resulting in a total of nine models. Subject ID was used as the subject identifier, and the day in the study was the repeated measures index. A compound symmetry repeated measures covariance structure was selected, as it improved the Bayesian information criterion (BIC) and Akaike information criterion (AIC) for model performance beyond the AR (1) autoregressive covariance structure. For main analyses, daily GWI symptom severity was entered as the dependent variable. For all analyses, the outcome variable was derived by taking a mean of the last 14 days of daily symptom severity reports for each participant during each condition (placebo, lower dose, higher dose). This was consistent with the registered analysis plan, in order to allow the botanicals time to exert clinical effects. A

restricted maximum likelihood (REML) estimation approach was used. Post hoc contrasts were carried out with the least-squares differences method. Significance for all tests was set at p < 0.05.

Sample size was determined with a-priori power analyses conducted in G*Power 3 [44]. The botanical trials were powered to detect a medium effect (Cohen's d = 0.5) with 0.99 power at a p = 0.05 level of significance. Ten individuals were needed to reach 0.99 power, due to the large number of repeated outcome assessments (56 per participant, repeated measures correlation of 0.5). The trials were not powered to detect small (Cohen's d = 0.25) effects, with only 0.42 predicted power. Small effects, however, were not expected to have important clinical impacts on GWI.

A Placebo-Controlled, Pseudo-Randomized, Crossover Trial of Botanical Agents for Gulf War Illness: Resveratrol (Polygonum cuspidatum), Luteolin, and Fisetin (Rhus succedanea)

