All study visits were held at the CRU and were conducted once a month for 10 months after completion of the baseline period. Participants received kits at each visit containing a one-month

supply of either placebo or botanical capsules. Kidney and liver function were monitored with blood draws conducted at visits 4, 7, and 10. The following laboratory values were tested at those visits: sodium, potassium, chloride, bicarbonate, anion gap, glucose, blood urea nitrogen, creatinine, calcium, phosphorus, albumin, total protein, total bilirubin, direct bilirubin, indirect bilirubin, alkaline phosphatase, aspartate aminotransferase (AST), and alanine aminotransferase (ALT).

The same protocol (one month of placebo, one month of lower-dose botanical, and one month of higher-dose botanical) was completed for each botanical. For safety reasons, lower-dose conditions always preceded higher-dose conditions, allowing adverse effects to be detected before a higher dose of the agent was used. Only the study pharmacist was unblinded to the assigned botanicals. All other study staff were aware of the design condition order, but were blinded to the specific botanical taken by each participant. Participants were blinded to both the administration order (placebo, lower-dose, and higher-dose) and the botanical compounds.

Treatment adherence was monitored at each study visit. Each month, participants were instructed to return their blister packs. Study staff checked for any missed doses and discussed with participants the importance of adhering to the administration regimen. Participants were provided with the option of re-enrolling in the study after completing the protocol, such that they could be assigned up to a total of six out of the nine compounds.

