2.3. Study Protocol

Individuals were screened via an online questionnaire and phone interview, followed by an in-person screening conducted at UAB's Clinical Research Unit (CRU). Informed consent was obtained at the in-person visit, and blood samples were collected for further screening. As the screening involved blood tests, individuals provided informed consent before being determined eligible for participation. Therefore, several individuals who provided consent were not eligible to participate in the study. Consented individuals received a tablet device for completing daily symptom reports each evening for the duration of their study participation.

Before beginning capsules, all participants completed a baseline period of 30 days. This period served as the baseline for all botanicals taken by the participant. Participants then were pseudo-randomized to receive up to three of the nine study compounds, as seen in **Figure 1**. A pseudo-randomized procedure was used to avoid contraindications with the botanicals. Randomization was conducted by a pharmacist. The pharmacist in charge of blinding and randomization was not otherwise involved in the study. The research personnel were blinded to the botanicals assigned to each participant. For each botanical, participants completed 30 days of placebo capsules, 30 days of lower-dose botanical, and 30 days of higher-dose botanical. Participants were blinded to all aspects of the study (the protocol and botanicals assigned). Research personnel were blinded to the botanicals assigned, though they were aware that placebo occurred first, followed by lower-dose and higher-dose treatment.

[figure not shown]

Figure 1. Study event flow. Participants took three of the tested compounds in the following order: placebo, lower-dose botanical, and higher-dose botanical.

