2.6. Statistical Analyses

All analyses were conducted in SPSS version 24 (IBM Corp., Armonk, NY, USA). For each botanical, a linear mixed model (LMM) was created to test changes in the primary outcome. LMMs were used to accommodate the repeated outcome assessments in each condition, nested in each participant. Subject ID was the repeated-measures nesting variable, the repeated-measures index was the day in the study, and the repeated measures covariance type was compound symmetry. The predictor was study condition, which could take four values (baseline, placebo, lower-dose, and higher dose botanical). The last 14 days of each condition were included in the models. The final 14 days of the baseline condition at the beginning of participation were used as the baseline for all tested botanicals. Post hoc tests were conducted using least-squares differences. A p < 0.05 was used for all tests. The same statistical approach was used to test the secondary outcomes of pain and fatigue. Nine total models are presented in this report (three botanicals tested for the outcomes of GWI severity, pain and fatigue).

If a participant did not complete the protocol, any valid data were still used in statistical tests. However, data imputation of missing values was not used, and participants were not included if they never took the assigned botanical. Therefore, we did not use a complete intent-to-treat method for analysis.

The three trials were powered to detect within-person fixed effects for study condition (baseline, placebo, lower dosage and higher dosage). Detection of a medium effect size (Cohen's d = 0.5) was targeted at a threshold of p < 0.05. With 56 repeated outcome assessments per participant, and a repeated measures correlation of 0.5, it would require 10 individuals to achieve 0.99 power for the main effect test.

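### For six of nine botanicals the LSD contrasts are unadjusted and no dose-versus-placebo test is named: false-difference risk is about 9% per botanical ungated, or about 3% gated unless baseline alone differs

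*Combined protocol and SAP*

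**What the plan says.** The document holds three method reports, each covering three botanicals. All three model symptom severity with condition as a four-level factor whose first level is a no-capsule baseline.

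- **Curcumin, boswellia, maritime pine (section 2.7):** "Post hoc contrasts were carried out with the least-squares differences method. Significance for all tests was set at p < 0.05".
- **Reishi, stinging nettle, epimedium (section 2.6):** "Post hoc tests were conducted using least-squares differences", again at 0.05 for every test. On baseline: "The final 14 days of the baseline condition at the beginning of participation were used as the baseline for all tested botanicals". On sample size: "it would require 10 individuals to achieve 0.99 power for the main effect test".
- **Resveratrol, luteolin, fisetin (section 2.7):** the four conditions are compared, with 0.05 for all tests. No follow-up method and no pair of conditions is named.

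I read least-squares differences as the LSD procedure, which applies no multiplicity adjustment. No report says which pairs were tested, which pair decides efficacy, or whether contrasts were read only after a significant condition test. The curcumin report says of its 14-day window: "This was consistent with the registered analysis plan". That registered plan is not among the documents, so the gap is a gap in this text only.

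The order of conditions is fixed in all three reports: "This administration order was chosen for safety reasons" (curcumin report, 2.3); "For safety reasons, lower-dose conditions always preceded higher-dose conditions" (resveratrol report, 2.3); "For each botanical, participants completed 30 days of placebo capsules, 30 days of lower-dose botanical, and 30 days of higher-dose botanical" (reishi report, 2.3).

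**The concern.** The trial is titled placebo-controlled, so a reader will look for dose versus placebo and take a p-value below 0.05 as a 5% risk of a false difference for that botanical, or 2.5% for a false benefit. There are two doses, hence two chances.

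Four conditions give six pairs, and only two of them are dose versus placebo. The other pairs, and the condition test itself, can be significant without any botanical effect, for example because symptom ratings settle after the first month or change when capsules start. The text does not separate those results from the efficacy question.

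An omnibus gate would not fully settle this. It protects the contrasts when all four conditions are equal. If baseline alone differs, the gate can open for that reason, and dose versus placebo is then tested twice at 5%.

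**Working it through.** **Inputs from the documents.** Four conditions; compound symmetry; 10 participants per botanical; 56 ratings per participant (14 per condition); correlation 0.5; d = 0.5; alpha 0.05 (taken as two-sided). **Assumptions:** complete, balanced data and correct standard errors; the sizes of baseline step and drift are mine.

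**1. The plan's own power figure.** Repeated-measures ANOVA, f = d/2, λ = N·m·f²/(1−ρ), df = m−1 and (N−1)(m−1).
- d = 0.5: λ = 10·56·0.0625/0.5 = 70, df 55 and 495, power 0.997 (stated 0.99).
- d = 0.25: λ = 17.5, power 0.417 (stated 0.42).

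Both reproduce. They concern a test across 56 measurements, not a dose-versus-placebo contrast.

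**2. Ungated risk.** Under compound symmetry the two contrasts share the placebo mean and correlate at 0.5. The chance that at least one of two such standard normal statistics exceeds 1.96 in absolute value is 9.07%. The curcumin report describes the outcome both as daily ratings and as a 14-day mean, so I simulated both: 9.0% with one mean per condition (df 27) and 9.1% with daily ratings (df 547). In the direction of benefit it is 4.5%, against 2.5% for a single test.

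**3. Gated by the four-condition F test, no time trend.** The baseline step is in within-person SDs of a condition mean.

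| Baseline step | df 27 | df 547 |
|---|---|---|
| 0 (all equal) | 3.2% | 3.1% |
| 0.5 | 5.2% | 5.2% |
| 1 | 8.1% | 8.2% |
| 2 | 9.0% | 9.1% |

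Under the plan's inputs one such SD is √(0.5/14) = 0.19 of a daily-rating SD, so the three steps are about 0.09, 0.19 and 0.38 daily SD.

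**4. Two named contrasts, no trend.** Holm (smaller p against 0.025, then larger against 0.05) gives 4.6%. Dunnett (critical t 2.33 at df 27) gives 5.0%. Neither depends on the baseline mean.

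**5. Linear drift, no botanical effect (df 27).** For a first botanical, baseline is one month before placebo. For a third, two botanicals of three 30-day months come between (2·3·30 = 180 days), so the baseline and placebo months are seven apart.

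| Drift per month (within-person SD) | LSD ungated | LSD gated, first botanical | LSD gated, third botanical | Holm | Dunnett |
|---|---|---|---|---|---|
| 0.1 | 11% | 5% | 9% | 6% | 7% |
| 0.25 | 23% | 15% | 23% | 15% | 15% |

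**6. Power cost of adjusting.** Plan's inputs: noncentrality 0.5/√(2·0.5/(14·10)) = 5.92, so power exceeds 99.9% at both 0.05 and 0.025. If instead each condition counts as one mean (my assumption, not the plan's), a 0.5 SD effect at the higher dose is 0.5/√(1−r) within-person SDs:

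| Correlation r between condition means | LSD | Holm | Dunnett |
|---|---|---|---|
| 0.5 | 33% | 23–26% | 24% |
| 0.7 | 50% | 38–43% | 40% |
| 0.9 | 93% | 87–91% | 88% |

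The lower Holm figure is for an effect at the higher dose only; the upper is for an equal effect at both doses.

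**The case against.** **A gate is the more natural reading.** The contrasts are called post hoc, and the reishi report powers the main effect test. On that reading, with all four conditions equal, the risk is about 3%, below 5%. This stands as far as it goes. A reader might infer that a gated analysis also carries up to 9% as a matter of course. The documents do not support that: every gated figure above 3% needs baseline to differ, and no size for such a difference is given. A one-off step is plausible, because baseline is taken without capsules and the curcumin report (2.3) describes it as serving for habituation, but it remains an assumption. The long gap before a third botanical is a different mechanism, drift, and belongs with the drift figures.

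**Gated LSD can do as well as Holm under drift.** True for a first botanical (5% and 15%, against 6% and 15%). It fails for a third, where the distant baseline opens the gate and gated LSD returns to 9% and 23%.

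**Unadjusted LSD is not shown for all nine botanicals.** Correct. A reader might extend it to resveratrol, luteolin and fisetin, but that report names no contrast method. There the gap is only that no deciding contrast is stated.

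**Something may have been prespecified elsewhere.** Possible. The registered plan may name the contrast, so the documents do not support saying that none was ever prespecified.

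**The family of two is a choice.** Each contrast, read alone as a test of one dose, keeps its 5%. The family matters for a conclusion about the botanical. It is the narrowest relevant one: all six pairs give about 19–20% ungated.

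**Fixed order and covariance matter more.** This may be so, and adjustment cures neither. It does not excuse leaving the deciding contrast unnamed.

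**Conclusion.** The concern holds in a limited form, and the change should be made. For six botanicals the text follows a four-condition model with unadjusted contrasts and states no deciding contrast, gate or adjustment. For the other three no contrast is named.

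The size depends on a rule that the text does not give. Without a gate, two chances nearly double the 5% that a reader would assume. With a gate the level is held if all conditions are equal, and is lost if baseline alone differs by an assumed half within-person SD or more.

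About 9% is not an upper bound. It rests on the compound-symmetry model being right. As an illustration, an assumed subject-by-condition variance of 0.02 to 0.10 of the total raises the ungated daily-data figure to about 20–50%. Nor does any of this show that a particular reported difference is false. It shows that the stated significance level cannot be attached to a dose-versus-placebo claim without knowing how the contrasts were chosen.

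**What to change.** - For each of the nine botanicals, on overall GWI severity, name two efficacy contrasts: lower dose versus its placebo month, and higher dose versus its placebo month. Adjust them by Holm or Dunnett, with one method throughout.
- Label this as post hoc, because the text describes completed analyses, unless the registered plan already names these contrasts. If it does, cite it.
- State whether the condition test gated the LSD contrasts, and which contrasts were run in each report.
- Show contrasts with baseline as descriptive, and treat pain and fatigue as supportive.
- State that the adjustment controls multiplicity only. It does not remove bias from the fixed order of placebo, lower dose and higher dose, or errors from a wrong covariance model.

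The cost is wording and a re-analysis of existing data, plus some power per contrast: negligible under the plan's inputs, larger if each condition effectively supplies one mean per person.

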2.7. Statistical Analyses

SPSS Statistics for Windows, version 24 (IBM Corp., Armonk, NY, USA) was used to conduct analyses. Linear mixed models (LMM) were utilized to test differences in self-reported symptom severity between the four conditions. A separate model was tested for each of the three botanicals. Subject ID was entered as the subject identifier, with all individual longitudinal data nested within-person. The participant's day in the study was entered as the index variable for repeated measures. Compound symmetry was selected as the repeated measures covariance type. The AR (1) autoregressive covariance type was also considered, but it did not improve the Akaike information criterion (AIC) or Bayesian information criterion (BIC) for model performance. The dependent variable was daily GWI symptom severity (0–100). Treatment condition (baseline,

placebo, lower-dose, and higher-dose) was entered as a fixed factor. The last 14 days of each condition were selected for analyses to permit time for clinical effects of the treatments to occur. A restricted maximum likelihood (REML) estimation approach was used. Statistical significance was set at p < 0.05 for all tests. The secondary analyses were conducted using the same approach.

We performed a-priori power analyses using G*Power 3 [43] to estimate sample size. Each of the nine botanical trials was powered to detect a medium effect (Cohen's d = 0.5) at 0.99 power with p = 0.05 threshold for significance. Given 56 repeated outcome measurements per participant (with a repeated measures correlation of 0.5), each trial required 10 individuals to obtain 0.99 power. Our studies were not powered (0.42 predicted power) to detect small effects (Cohen's d = 0.25).

A Placebo-Controlled, Pseudo-Randomized, Crossover Trial of Botanical Agents for Gulf War Illness: Reishi Mushroom (Ganoderma lucidum), Stinging Nettle (Urtica dioica), and Epimedium (Epimedium sagittatum)

2. Materials and Methods

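### The stated powers at n=10 (0.99 for d=0.5 and 0.42 for d=0.25) cannot both hold for the planned 4-level condition test, so at least one is wrong for that test

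*Combined protocol and SAP*

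**What the plan says.** The combined document holds three reports, each covering three botanicals.

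- **Curcumin/boswellia/maritime pine, section 2.7.** Power was computed in G*Power 3 for d=0.5 at the 0.05 level: "Ten individuals were needed to reach 0.99 power, due to the large number of repeated outcome assessments (56 per participant", with a repeated-measures correlation of 0.5. It adds: "The trials were not powered to detect small (Cohen's d = 0.25) effects, with only 0.42 predicted power".
- **Resveratrol/luteolin/fisetin, section 2.7.** Same inputs: "Given 56 repeated outcome measurements per participant (with a repeated measures correlation of 0.5", 10 people, 0.99 power. It also says "Our studies were not powered (0.42 predicted power) to detect small effects".
- **Reishi/stinging nettle/epimedium, section 2.6.** Same d, 56 assessments, correlation 0.5, n=10 and 0.99. Here the target is explicit: the main effect of study condition, which takes four values. It does not give the 0.42.

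All three fit condition (baseline, placebo, lower dose, higher dose) as the fixed factor under compound symmetry. Day in study is only the repeated-measures index, and no test of a day factor is planned.

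On the outcome unit, the curcumin report says that "daily GWI symptom severity was entered as the dependent variable" and then that "the outcome variable was derived by taking a mean of the last 14 days of daily symptom severity reports". The resveratrol report says "The dependent variable was daily GWI symptom severity". The reishi report says "The last 14 days of each condition were included in the models" and describes no averaging.

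**The concern.** A condition factor with four values has 3 numerator df, however many days are recorded per condition. The explanation given for needing only ten people, the 56 assessments, suggests that the number of days may have been entered as the number of factor levels. That would be power for a different hypothesis.

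The 0.99 is the stated justification for ten people per botanical in all three reports. The 0.42 is what two reports offer to a reader judging whether a null result could hide a small effect. If the two figures do not belong to the planned test, neither use is secure until they are recalculated.

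**Working it through.** **Inputs from the documents:** n=10; 56 measures (4 conditions × 14 days); ρ=0.5; alpha 0.05; d=0.5 and 0.25; 4 conditions; compound symmetry. **Assumed:** f=d/2 and sphericity in step 1; the SD to which d refers and the pattern of the four means in steps 3 and 4. None of these is stated.

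**1. Reproducing the stated pair.** For a within-person factor with m levels, λ = f²·n·m/(1−ρ), on m−1 and (n−1)(m−1) df. With m=56 the df are 55 and 495.

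- d=0.5: λ = 0.25²×10×56/0.5 = 70, power 0.997.
- d=0.25: λ = 0.125²×10×56/0.5 = 17.5, power 0.417.

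The same calculation at neighbouring n:

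| n | d=0.5 | d=0.25 |
|---|---|---|
| 8 | 0.978 | 0.315 |
| 9 | 0.991 | 0.365 |
| 10 | 0.997 | 0.417 |
| 11 | 0.999 | 0.469 |

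Only n=10 gives 0.42. However, n=9 already reaches 0.99, so this route does not explain why ten were said to be needed. With m=4 and otherwise the same inputs, the pair is 0.39 and 0.12.

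**2. Can any 3-df test have both figures?** λ is proportional to d², so halving d divides λ by 4. SD, ρ and mean pattern scale both λ values equally and drop out.

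| df | λ for 0.99 at d=0.5 | power at λ/4 | λ for 0.42 at d=0.25 | power at 4λ |
|---|---|---|---|---|
| 3, 27 | 27.3 | 0.512 | 5.47 | 0.967 |
| 3, 547 | 23.7 | 0.509 | 4.78 | 0.968 |

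Rounding does not close the gap: starting from 0.985 still gives 0.48 at d=0.25. A 1-df contrast fails too: 0.99 pairs with about 0.57, and 0.42 with about 0.94.

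**3. Planned test on daily rows.** Set total daily variance to 1, so that ρ=0.5 makes the within-person variance 0.5. The denominator df are 560−10−3 = 547. For four means with largest difference d, f² = c·d² and λ = 560·c·d²/0.5 if d is in total daily SD, or 560·c·d² if d is in within-person SD.

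| Mean pattern | c | Total SD: d=0.5 / 0.25 | Within-person SD: d=0.5 / 0.25 |
|---|---|---|---|
| Two versus two (f=d/2) | 1/4 | >0.999 / 0.952 | 0.9996 / 0.694 |
| One different | 3/16 | >0.999 / 0.872 | 0.995 / 0.556 |
| Evenly spaced | 5/36 | >0.999 / 0.745 | 0.970 / 0.427 |
| Minimum variability | 1/8 | >0.999 / 0.694 | 0.952 / 0.387 |

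The dose-versus-placebo contrast (140 rows per condition, 547 df) has >0.999 / 0.840 in total SD and 0.987 / 0.551 in within-person SD.

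**4. If d and ρ describe the 14-day means themselves** (4 values per person, 3 and 27 df), λ = 40·c·d²/0.5. Over the same four patterns the condition test has 0.21 to 0.39 at d=0.5 and 0.08 to 0.12 at d=0.25. The contrast on the model's 27 df has 0.33 and 0.12.

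**5. Person-by-condition variance.** Steps 3 and 4 assume none beyond the stated correlation structure. Suppose 20% of the within-person variance (0.1 of 0.5) is person-by-condition variance, leaving 0.4 between days. With no true effect, the condition mean square then has expectation 14×0.1+0.4 = 1.8. The pooled residual has expectation (27×1.8+520×0.4)/547 = 0.47. Simulation gives the 3/547-df test a type I error of about 0.56.

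**The case against.** **The practical error may be small.** On daily rows with d in within-person SD and evenly spaced means, the pair is 0.970 / 0.427, about two points from the printed 0.99 and within one point of 0.42. Most of the text supports daily rows: the 56 assessments, day as the repeated index, the daily dependent variable, and the absence of averaging in the reishi report. On that reading 0.99 is roughly met or exceeded. The curcumin report uses 0.42 only to set aside small effects, which it regards as clinically unimportant. All of this stands and limits the size of the point. It does not make the two figures compatible on 3 df.

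**The route to the figures is inferred.** No G*Power test or d-to-f conversion is stated, and n=9 would already have met the target. This stands. The incompatibility in step 2 does not depend on the route.

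**The figures record what was calculated beforehand.** That is fair, so new values should be labelled as a recalculation. The record still needs correcting where it attributes 0.99 to the condition main effect.

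**Stronger readings.** A reader might infer that ten people were too few. The documents do not support this, because daily-row power at d=0.5 is 0.95 or more in every case tried. The low values in step 4 require ρ=0.5 to describe 14-day means, whereas the reports attach it to the 56 assessments. A reader might also infer that 0.42 is simply too low. That holds under the favourable f=d/2 pattern (0.69 to 0.95), but over the four patterns and both SDs the range is 0.39 to 0.95, which contains 0.42.

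**Conclusion.** The point holds. The two stated powers cannot both be right for the 3-df condition test that the reishi report names, nor for a 1-df contrast. This rests only on λ being proportional to d². That the figures came from a 56-level factor is a close numerical match, not a documented fact.

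Which figure is wrong, and by how much, depends on inputs that the reports omit. The gap ranges from about two points to a large one in either direction. The outcome-unit contradiction in the curcumin report is a separate wording fault, but it must be settled before either figure can be recalculated. The daily-row values also assume no person-by-condition variance; the 20% share is an illustration, not an estimate from the documents. The point should be fixed, but it is not evidence that the trials were underpowered.

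**What to change.** 1. Reconcile the outcome unit in section 2.7 of the curcumin report with the other two reports.
2. State the SD and the level (days or 14-day means) to which d and ρ refer, the pattern of means, and the test used for the power calculation.
3. In all three reports, give as a recalculation the power at n=10 of the 3-df condition test and of the dose-versus-placebo contrast on the mixed model's df. Give ranges over SD and mean pattern, not one favourable case. On daily rows with compound symmetry and ρ=0.5, the condition test has 0.95 to >0.99 at d=0.5 and 0.39 to 0.95 at d=0.25; the contrast has 0.99 to >0.99 and 0.55 to 0.84. If d and ρ describe 14-day means, use the values in step 4.
4. State that the daily-row figures assume no person-by-condition variance, and show the sensitivity, labelled as an assumption. The caveat applies to daily rows and cannot be confined to 14-day means.

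The cost is wording and a few recalculated figures per report, with no new data or participants. The downside is that the stated power becomes conditional on named inputs and may look less favourable.
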